### 12.3.3 Microbiology laboratory quality control

Details of the arrangements for laboratory quality control (QC) are found in the STREAM Laboratory Manual.

ITM Antwerp will assess and prepare all laboratories before start of the trial, and assure quality of the sites' microscopy and cultures throughout the trial and GeneXpert MTB/RIF and/or LPA during the screening. Test performance will be periodically monitored and reported.

The following QC procedures will be used:

- Microscopy: internal control of newly prepared lots of staining solutions at the sites, together with random checking of smears performed at the presumed end of the intensive phase.
- Cultures: monitoring of false negative and contamination rates.
- LPA DST: a water blank in each run, to check for cross-contamination; strip-inbuilt controls for QC of amplification and colour reaction. EQA will be performed by sending panels composed of bacilli suspensions with known resistance patterns (Proficiency Testing).
- GeneXpert MTB/RIF: monitoring of errors plus proficiency testing panels will be used for the sites. There will be QC of phenotypic DST, DNA sequencing of resistance-conferring mutations performed at the central laboratory in Antwerp.

Details of QC will be provided in the laboratory manual.

# 12.4 Central monitoring

Central monitoring of data at MRC CTU will be conducted by CRF review, with appropriate and range and consistency checks programmed into the database. MRC CTU will raise any concerns they may have about the data captured by use of query forms sent to the site, as detailed in the Data Management Plan.

The Trial Master File will be stored at MRC CTU and at Vital Strategies and will be maintained by the TM throughout the trial. All trial specific documents will be centrally tracked and copies obtained from the sites for all communication with regulatory bodies. Details about maintaining trial files and any other monitoring that will be carried out centrally are in the Monitoring Plan, other study documentation and plans as appropriate.

# 13 SAFETY REPORTING

GCP requires that both investigators and sponsor follow specific procedures when notifying and reporting adverse events/reactions in clinical trials. These procedures are described in this section of the protocol. Section 13.1 lists definitions, section 13.2 gives details of the institution/investigator responsibilities and section 13.3 provides information on MRC CTU responsibilities.

AEs are collected from the time the informed consent form is signed at screening until follow-up is completed or the participant withdraws from the trial. If a patient is found to be ineligible for the trial at screening, or chooses not to be randomised, no further AE data should be collected from that point.

### 13.1 Definitions

The definitions of the EU Directive 2001/20/EC Article 2 based on GCP apply in this protocol. These definitions are given in Table 11.

**Table 11: Safety reporting definitions** 

Term	Definition
Adverse Event (AE)*	Any untoward medical occurrence in a patient or clinical trial
	participant to whom a medicinal product has been administered
	including occurrences which are not necessarily caused by or related
	to that product.
Adverse Reaction (AR)	Any untoward and unintended response to an investigational
	medicinal product related to any dose administered.
Unexpected Adverse	An adverse reaction, the nature or severity of which is not consistent
Reaction (UAR)	with the information about the medicinal product in question set out
	in the summary of product characteristics (or Investigator brochure)
	for that product.
Serious Adverse Event	Respectively any adverse event, adverse reaction or unexpected
(SAE) or Serious Adverse	adverse reaction that:
Reaction (SAR) or	Results in death
Suspected Unexpected	Is life-threatening**
Serious Adverse Reaction	Requires hospitalisation or prolongation of existing
(SUSAR) (see 13.2.1 (d)	hospitalisation***
for causality definition)	Results in persistent or significant disability or incapacity
	Consists of a congenital anomaly or birth defect
	Other medically important condition, including suspected
	transmission of any infectious agent via administration of a
	medicinal product;
	
 
Is a combination of the above (to be specified).
 

# 13.1.1 Clarifications and exceptions

\*In addition, events from the point that the participant gives informed consent/assent to screening until randomisation are also defined as AEs for patients in stage 2.

\*\*The term 'life-threatening' in the definition of 'serious' refers to an event in which the patient was at risk of death at the time of the event; it does not refer to an event which hypothetically might have caused death if it were more severe.

\*\*\*Hospitalisation is defined as an inpatient admission, regardless of length of stay, even if the hospitalisation is a precautionary measure for continued observation. Hospitalisations for a pre-existing condition that has not worsened (including elective procedures) do not constitute an SAE; nor do hospital admissions for social and not medical reasons. Due to the seriousness of the disease in this study, some patients may be admitted to hospital for the initial phase of their trial treatment. This would not qualify as an SAE, although if that hospitalisation had to be prolonged beyond the normal length of admission, then it would be an SAE.

Medical judgement should be exercised in deciding whether an AE/AR is serious in other situations. Important AE/ARs that are not immediately life-threatening or do not result in death or hospitalisation but may jeopardise the participant or may require intervention to prevent one of the other outcomes listed in the definition above, should also be considered serious.

### 13.1.2 Trial specific exceptions to expedited SAE notification and reporting

Data on disease relapse or progression are collected as part of the primary outcome of the trial and are not considered to be SAEs, unless fatal or in stage 2, requires hospitalisation. QT prolongation does not require grading since the actual QT and QTcF values are collected as part of routine monitoring, but QT or QTcF prolongation to more than or equal to 500 ms should be recorded as a notable event as specified in 13.1.3. Planned hospitalisations for the initial phase of trial treatment are also not considered as SAEs as noted in section 13.1.1 above.

In Stage 2, adverse events which are not serious should be reported on the Stage 2 AE log. However, abnormal laboratory results that are not deemed by the PI to be clinically significant or do not result in change in therapy are exempt from event reporting i.e. they do not need to be added to the AE log. A clinically significant lab value is one that indicates a new disease process, an exacerbation or worsening of an existing condition, or requires further action(s) to be taken.

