# 8.3 Procedures for assessing safety

Throughout this study, patients will be closely monitored for signs and symptoms of drug toxicity. All toxicities leading to the study therapy being temporarily or permanently discontinued and all Grade 3 or greater toxicity effects will require thorough investigation with relevant clinical and laboratory tests, as clinically indicated.

These should be repeated as needed until final resolution or stabilisation of the toxicity; if this is after the end of the trial, follow-up will be the responsibility of the treating clinician. All symptoms and laboratory findings will be graded according to severity using DAIDS criteria. Laboratory events will be reported as adverse events only if clinically significant. If the patient has a medical diagnosis at randomisation whose signs or symptoms worsen during the study to a Grade 3 or greater, this is a notable event (NE) that must be reported. Other notable events and SAEs will be reported as they occur to the MRC CTU, as well as to other bodies required to be notified in each country. For details of safety reporting see Section 13.

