# 8.5 Changes to treatment or follow-up

## 8.5.1 Interruptions to treatment

The treatment regimens or selected drugs may be interrupted at the discretion of the local PI or treating clinician:

- For a serious adverse event
- For a QT or QTcF measurement of more than or equal to 500ms
- If ALT/AST rise to more than or equal to 5 times ULN, or if AST/ALT rise to more than or equal to 3 times ULN in the presence of a total bilirubin rise to more than or equal to 2 times ULN
- If the investigator decides to withhold treatment in the interest of the safety and well-being of the participant.

If treatment is interrupted for a suspected serious drug reaction, attempts should be made to identify the drug concerned. Further guidance on expected toxicities is provided in the STREAM Patient Management Guide. After resolution of the suspected adverse reaction, treatment may be gradually re-introduced until the allocated regimen has been re-instituted.

If treatment with one of the core drugs other than bedaquiline (i.e. kanamycin or amikacin, isoniazid, moxifloxacin or levofloxacin, and clofazimine) is missed in either the intensive or continuation phase of one of the study regimens this can be made up by extending this phase of the regimen by the number of treatment days missed at the discretion of the treating physician and in the absence of ongoing toxicity.

Bedaquiline treatment interruptions will be handled separately to those involving the other core drugs, and are managed based on the phase of bedaquiline dosing:

- Treatment interruptions during the 14-day loading period:
  - All treatment interruptions during the loading phase of bedaquiline must be reported to the clinical team at the MRC CTU within one working day of the site becoming aware, and advice will be given on a case by case basis

- For interruptions of less than or equal to 14 days, bedaquiline loading should resume at the point of the last dose to complete the total doses required in the loading period with the doses previously received taken into account
- For interruptions of >14 days, treatment should be re-started at the beginning of the loading period. The full 14 days of loading should be completed with no accounting for doses taken already
- Only one treatment interruption is allowed during the loading phase and restarting treatment is not permitted after interruptions of >30 days
- Treatment interruptions during the thrice-weekly maintenance dosing period:

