### 13.1.3 Additional notable events

The following notable events should also be identified and reported to the MRC CTU within the same time frame as an SAE (unless they also meet the criteria for an SAE, in which case they should be reported as such):

- Pregnancy in a patient or partner of a patient during protocol treatment or follow-up
- QT or QTcF measurement more than or equal to 500 ms while on treatment
- ALT/AST more than or equal to ten times ULN, or ALT/AST more than or equal to three times ULN in the presence of total bilirubin more than or equal to 2 times ULN
- Creatinine kinase more than or equal to 10 times ULN
- Pancreatic amylase more than or equal to 2 times ULN
- The occurrence of any grade 3 or higher adverse event
- Any toxicity that leads to withholding or stopping of allocated treatment for more than 24 hours
- A clinically significant dysrhythmia, such as an episode of ventricular tachycardia, with three or more irregular beats in a row.
- An overdose of trial medication.

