This analysis will be conducted on the whole study period, and separately for follow-up censored at Week 76. It will also be repeated comparing bedaquiline and non-bedaquiline regimens (Regimens A and B vs C and D) and comparing Regimen B_{mox} and Regimen C, and Regimen B_{lev} and Regimen C. A descriptive analysis will consider deaths by cause, as adjudicated by an independent review committee. In addition to the comparisons detailed above, analyses of the whole study period (up to Week 132) will include comparisons of Regimen C with Regimen D. Comparisons of Regimen C and Regimen D using data up to Week 76 were carried out at the time of the primary analysis but considered exploratory.

7.2.3 Proportion of patients experiencing a grade 3 or greater adverse event, as defined by the DAIDS criteria, during treatment and follow-up

The difference in proportion of patients experiencing a grade 3 or greater adverse event, as defined by the DAIDS criteria¹⁰, during treatment and follow-up, between Regimen B and Regimen C, between Regimen B_{mox} and Regimen C, between Regimen B_{lev} and Regimen C, between Regimen B and Regimen D, and between Regimen B and Regimen A, with corresponding two-sided 95% confidence intervals and p-values will be estimated (see Section 6.1.1). The analysis will be stratified by randomisation protocol (as defined in Section 1.6) and HIV status with three strata: HIV negative, HIV positive with CD4 count less than 350 cells/mm³, and HIV positive with CD4 count more than or equal to 350 cells/mm³.

This analysis will be conducted on the whole study period, the study period censored at Week 76, and separately for each phase (Treatment censored at Week 76, and Allocated treatment).

Comparisons will be repeated in subgroups according to HIV infection status. In addition the proportion of participants with cardiac events, hearing loss and hepatotoxicity by Week 76 and Week 132 in Regimen C and Regimen D will be compared to Regimen B.

In addition to the comparisons detailed above, analyses of the whole study period (up to Week 132) will include comparisons of Regimen C with Regimen D. Comparisons of Regimen C and Regimen D using data up to Week 76 were carried out at the time of the primary analysis but considered exploratory.

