9.3.4 Weight gain

Patient weight will be tabulated by treatment arm and visit in addition to change from baseline weight by visit and treatment arm.

9.3.5 **SAE/NE/AE**

SAEs and grade 3 or higher AEs will be tabulated by MedDRA System Organ Class (SOC) / Standardised MedDRA queries (SMQ) and Preferred Term and treatment arm. NEs will be tabulated by event type and treatment arm. The total number of events and the number of participants with at least one event will be given. SAEs will also be tabulated by event relatedness to study drugs and treatment arm. Pregnancy outcomes will be reported by treatment arm.

Grade 3 and 4 laboratory AEs will be tabulated by laboratory marker and treatment arm. This will be presented for results from the central laboratory alone.

These analyses will be conducted on the whole study period, and separately for each phase (Treatment censored at Week 76, and Allocated treatment).

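### Protocol 13.1.2 exempts a clinically significant laboratory result from the Stage 2 AE log when therapy is unchanged, in conflict with 8.3, and SAP 7.2.3 does not say whether the grade 3+ endpoint relies on that log

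*Protocol*

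**What the plan says.** Three protocol sections bear on whether a laboratory abnormality becomes a recorded event.

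- **Section 8.3:** "Laboratory events will be reported as adverse events only if clinically significant". It states no other condition.
- **Section 13.1.2, Stage 2:** "adverse events which are not serious should be reported on the Stage 2 AE log". It then makes an exception for laboratory findings: those "not deemed by the PI to be clinically significant or do not result in change in therapy are exempt from event reporting". The next sentence defines a clinically significant value broadly: a new disease process, a worsening of an existing condition, or a need for any further step.
- **Section 13.1.3:** some laboratory findings are notable events whatever is done about treatment. The first is "ALT/AST more than or equal to ten times ULN". The others are ALT/AST at 3 times ULN or more with bilirubin at 2 times ULN or more, creatine kinase (printed as creatinine kinase) at 10 times ULN or more, and pancreatic amylase at 2 times ULN or more. A general item covers adverse events of grade 3 or above.

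In the SAP, 7.2.3 compares the proportion of patients with a grade 3 or greater adverse event. It also compares "the proportion of participants with cardiac events, hearing loss and hepatotoxicity by Week 76 and Week 132". It names no data source for the laboratory part of either. SAP 5.8 gives treatment-emergence rules for all adverse-event analyses. SAP 9.3.5 tabulates grade 3 and 4 laboratory events by marker and says: "This will be presented for results from the central laboratory alone".

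**The concern.** Protocol 1.1.9 says that the treating clinician knows the allocation, and 8.5.1 leaves interruption of treatment to the discretion of the local PI or treating clinician. If a laboratory result is logged only when therapy changes, the same value can be an adverse event in one patient and unrecorded in another, depending on an unblinded decision.

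Protocol 2.2.1 names different expected toxicities for the regimens: liver and pancreas for bedaquiline, kidney and hearing for kanamycin. Readiness to change therapy for a given value could therefore differ by arm. What is at stake is the comparability of logged grade 3+ laboratory events between Regimens C (or D) and B. In Stage 2 this is a secondary outcome (Protocol 3.3.2).

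**Working it through.** No sample size, power or error rate is involved, so the check sets the rules side by side.

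**Step 1. The two logging rules, for a non-serious abnormal result**

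| PI's judgement | Therapy changed? | 8.3 | 13.1.2 as written | 13.1.2 with 'and' |
|---|---|---|---|---|
| Not significant | No | Not reported | Exempt | Exempt |
| Not significant | Yes | Not reported | Exempt | Logged |
| Significant | No | **Reported** | **Exempt** | Logged |
| Significant | Yes | Reported | Logged | Logged |

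As written, the sections disagree on one row: significant, therapy unchanged. With 'and' that row agrees. The second row then differs on paper, but it is empty under 13.1.2's own definition, because a change in therapy is itself a further step and so makes the value significant.

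**Step 2. What 13.1.3 recovers**

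The named thresholds cover marked or bilirubin-accompanied transaminase rises, creatine kinase and amylase. The Stage 2 panels in Protocol 8.2 also include serum creatinine, electrolytes and blood counts, and 13.1.3 has no threshold for any of these. Nor does it have one for ALT/AST from 5 to below 10 times ULN without raised bilirubin. The general grade 3+ item helps only if an exempt result still counts as an adverse event, which the text leaves unclear. The item on withholding or stopping treatment for more than 24 hours again depends on the treatment decision.

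**Step 3. A worked case**

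Take a non-serious ALT of 6 times ULN with normal bilirubin, judged clinically significant. Section 8.5.1 lists "If ALT/AST rise to more than or equal to 5 times ULN" as a ground on which treatment may be interrupted.

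- Treatment interrupted (taken here as a change in therapy, a term the protocol does not define): the result is logged.
- Treatment continued: the result is exempt from the log under 13.1.2, is below the 10-fold notable-event threshold (6 < 10), and does not meet the combined bilirubin item. Section 8.3 would still report it.

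The documents do not reproduce the DAIDS cut-offs, so the case rests on the 5-fold and 10-fold limits, not on a grade.

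**Step 4. What feeds the endpoint**

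- *Pointing to measured values:* SAP 5.8 uses the maximum grade within phase, counts shifts from abnormally low to abnormally high, and handles day-1 laboratory events by the timing of the blood sample. SAP 9.3.2 tabulates liver tests by grade and visit and counts patients at 5 times ULN or more. SAP 9.3.5 uses central-laboratory results for its laboratory table.
- *Pointing to logged events:* SAP 7.2.1 places adverse events by start date and has rules for partial or missing dates, which suits a log better than dated samples. The central-laboratory table in 9.3.5 stands apart from the MedDRA table of grade 3+ events and is not said to feed 7.2.3.

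Two analysts could reasonably build different endpoints from this text.

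**The case against.** The strongest reply is that the analysis does not need the log. SAP 5.8 applies to all adverse-event analyses and its laboratory rules read as value-based. Laboratory assessments are blind (Protocol 1.1.9), and the SAP supersedes the analysis text in the protocol. An ALT of 6 times ULN is counted in SAP 9.3.2 whatever the clinician does. The source may also be stated in the Extensive Stage 2 SAP, which is not among the documents. Much of this stands: a reader might infer that the safety endpoint *does* depend on an unblinded treatment decision, and the documents do not establish that. They leave it open, because 7.2.3 names no source.

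Second, 13.1.2 says that exempt results need not go on the log, not that they cease to be adverse events. A grade 3+ result might therefore still be a notable event. That reading is possible, but the quoted words exempt such results from event reporting generally, so a site cannot tell. A reader might also infer that every laboratory abnormality escapes reporting when therapy is unchanged. The named thresholds in 13.1.3 show otherwise.

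Third, 'only if' in 8.3 is strictly a necessary condition, so an added therapy condition would not formally contradict it. But 8.3 states no second condition. The broad definition of significance in 13.1.2 would also serve little purpose if a change in therapy were required as well.

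Fourth, changing 'or' to 'and' still leaves clinical significance to the same unblinded investigator. This stands, and is why the SAP statement is needed too.

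**Conclusion.** The inconsistency is real and confined to one case: a clinically significant, non-serious laboratory result with therapy unchanged is reportable under Protocol 8.3 and exempt under 13.1.2. The notable-event list closes part of the gap but leaves creatinine, electrolytes, haematology and isolated ALT/AST from 5 to below 10 times ULN. For these, logging can depend on the decision of a clinician who knows the arm. The secondary grade 3+ comparison may be affected to the extent that it draws on the log.

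The size cannot be derived from the documents. A reader might try to put a number on it. Suppose 8% to 20% of patients per arm have a laboratory-only grade 3+ event, and therapy changes after 30% of these in one arm and 40% to 50% in the other. The spurious difference would run from 8% × (0.40 − 0.30) = 0.8 points to 20% × (0.50 − 0.30) = 4.0 points. The standard error, at a rate of 48% and 200 per arm, is √(2 × 0.48 × 0.52 / 200) = 5.0 points. None of the laboratory-only shares or therapy-change rates is in the documents, and the sum assumes no capture by notable-event forms or measured values. It is not an estimate of bias in this trial.

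**What to change.** **Protocol 13.1.2:** replace 'or' with 'and', so that only results that are neither clinically significant nor followed by a change in therapy are exempt. Reconcile the sentence with 8.3, and say whether an exempt result can still be a notable event under the general grade 3+ item in 13.1.3.

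**SAP 7.2.3:** state that the laboratory part of the grade 3+ endpoint is derived from graded measured values under the SAP 5.8 rules, whether or not logged, for the period of scheduled sampling to Week 76. The whole-study analysis should also keep later clinically indicated results and logged events, because Protocol 8.2 ends routine testing at Week 76. Say which laboratories contribute, since 8.2 allows qualified local laboratories while the SAP 9.3.5 table is central only. Name the source for hepatotoxicity in the same place. Give a log-only version as a sensitivity analysis.

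**Cost:** one word and a cross-check in the protocol, and a short paragraph in the SAP using data already collected. The SAP change also works for patients whose logging is complete. The downside is a somewhat higher grade 3+ rate in every arm, because some results never logged will count. Laboratory events after Week 76 will still depend on clinically indicated testing.
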